3.3 Trial Population

3.3.1 Number of Subjects and Description of Population

A total of approximately 720 male and female subjects with a current diagnosis of ADHD are anticipated to be enrolled with the expectation that at least 300 subjects will achieve 6-month exposure and 100 subjects will achieve 52-week exposure.

The trial population will include approximately 560 completing rollover subjects from double-blind phase 3 trials (ie, Trial 405-201-00013 or Trial 405-201-00014) and approximately 145 de novo subjects between the ages of 18 and 55 years, inclusive, at the time of informed consent; de novo subjects must meet the DSM-5 criteria for ADHD including predominantly inattentive presentation, hyperactive presentation, or combined presentation) as confirmed by the ACDS Version 1.2. To confirm that ADHD is the primary diagnosis, the Mini International Neuropsychiatric Interview (MINI) will be used to identify and exclude other psychiatric conditions which would preclude enrollment.

Confidential - Proprietary Information

31

De novo subjects must washout of any prohibited medications prior to baseline (Table 4.1-2). Rollover subjects have already met the diagnostic criteria for ADHD (ie, DSM-5 criteria for ADHD as confirmed by the ACDS Version 1.2) as a part of their screening for the double-blind phase 3 trial (ie, Trial 405-201-00013 or Trial 405-201-00014) and have already been washed out of any prohibited medications prior to the start of the double-blind trial treatment phase, which will be confirmed prior to baseline of Trial 405-201-00015 via concomitant medication reporting and urine drug screening.

Subjects who roll over from Trial 405-201-00013 or Trial 405-201-00014 who turned 56 years old during that trial are also permitted to enroll in this trial.

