3.5 Endpoints

3.5.1 Primary Endpoint

The primary endpoint in this trial is the long-term safety and tolerability of centanafadine SR tablets administered BID (400 mg TDD), as assessed by the frequency and severity of treatment-emergent adverse events (TEAEs).

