7.1 Sample Size

The sample size is not based on statistical power considerations but on ICH/GCP requirements. The trial population will be derived from eligible subjects from the, double-blind phase 3 trial (ie, Trial 405-201-00013 or Trial 405-201-00014) and de novo subjects from selected sites. It is expected that approximately 560 completing rollover subjects from double-blind phase 3 trial (Trial 405-201-00013 or Trial 405-201-00014) and approximately 145 de novo subjects will be enrolled into this trial.

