7.4 Primary, Secondary, and Exploratory Endpoint Analyses

7.4.1 Primary Endpoint Analysis

The primary (safety) endpoint analysis is the frequency and severity of AEs (including evaluations of rash and abuse potential) in the open-label treatment period. All AEs will be coded using the MedDRA PTs. The incidence of TEAEs will include the following summaries:

- TEAEs
- TEAEs by severity
- TEAEs potentially causally related to the IMP
- TEAEs with an outcome of death
- Serious TEAEs
- TEAEs leading to discontinuation of the IMP
- Abuse-related AEs and AEs involving medication handling irregularities

A TEAE is defined as an AE that starts after the first dose of IMP or an AE that is reported at baseline and increases in intensity or becomes serious or trial drug-related or results in death, discontinuation, interruption, or reduction of IMP.

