## 9 Safety Analysis

The primary safety endpoint analysis is the frequency and severity of AEs in the open-label treatment period (see Section 9.1). Other standard safety variables to be analyzed include clinical laboratory tests, vital signs, body weight, waist circumference, BMI, 12-lead electrocardiograms (ECGs), and physical examinations. In addition, data from the following safety scales will be evaluated: C-SSRS and Study Medication Withdrawal Questionnaire (SMWQ).

Safety analyses will be conducted based on the Safety Sample, and summary statistics will be provided by parent study treatment group for rollover subjects, de novo subjects and overall, unless otherwise indicated.

Unless otherwise specified, in general, analysis of safety data will be performed on observed case and for last visit.

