#### 9.1 Adverse Events

All adverse events will be coded by System Organ Class (SOC) and Preferred Term (PT) according to the Medical Dictionary for Regulatory Activities (MedDRA). AEs that are sexspecific, e.g., ovarian cancer, will have their incidence rates evaluated for the specific sex.

Treatment-emergent AEs (TEAEs) are defined as AEs with an onset date on or after the first dose of IMP. In more detail, TEAEs are all adverse events which started after start of IMP; or if the event was continuous from baseline and was worsening, serious, study drug related, or resulted in death, discontinuation, interruption or reduction of study therapy. Adverse events occurring up to 30 days after the last day of IMP will be included in the summary tables.

The incidence of the following events in the open-label treatment phase will be summarized using the Safety Sample:

- a) Treatment-emergent AEs (TEAEs)
- b) TEAEs by severity
- c) TEAEs potentially causally related to the IMP
- d) TEAEs with an outcome of death
- e) Serious TEAEs
- f) TEAEs leading to discontinuation of the IMP
- g) Treatment-emergent Adverse Events of Special Interest (AESI)
- h) Abuse-related TEAEs and TEAEs involving MHIs (Medication handling irregularities)

AEs will be classified by Primary SOC and PT according to the MedDRA. AEs that are gender-specific, e.g., ovarian cancer, will have their incidence rates evaluated for the specific gender.

Incidence of TEAEs will be summarized for the open-label treatment period. Incidence of TEAEs by SOC and MedDRA PT will be summarized for sex and race.

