#### Clinical Study Report 405-201-00015

SAP 405-201-00015

- CT-7.2 Number and Percentage of Subjects Receiving Study Medication and Mean and Range of Average Daily Dose (Safety Sample)
- CT-8.1 Adverse Events (All Causalities) (Safety Sample)
- CT-8.2.1 Incidence of TEAEs by System Organ Class and MedDRA Preferred Term (Safety Sample)
- CT-8.2.2 Incidence of TEAEs B by System Organ Class, MedDRA Preferred Term and Severity (Safety Sample)
- CT-8.2.3 Incidence of TEAE of at Least 5% by System Organ Class and MedDRA Preferred Term (Safety Sample)
- CT-8.2.4 Incidence of TEAEs by System Organ Class and MedDRA Preferred Term, by Sex (Safety Sample)
- CT-8.2.5 Incidence of TEAEs by System Organ Class and MedDRA Preferred Term, by Race (Safety Sample)
- CT-8.2.6 Incidence of Non-Serious TEAE of at Least 5% by System Organ Class and MedDRA Preferred Term (Safety Sample)
- CT-8.2.7 Incidence of TEAE of at Least 2% by System Organ Class and MedDRA Preferred Term (Safety Sample)
- CT-8.2.8 Incidence and Occurrence (Number of Events) of Serious Treatment-Emergent Adverse Events by System Organ Class and MedDRA Preferred Term
- CT-8.2.9 Incidence and Occurrence (Number of Events) of Potentially Drug-Related Serious Treatment-Emergent Adverse Events by System Organ Class and MedDRA Preferred Term
- CT-8.2.10 Incidence and Occurrence (Number of Events) of Non-Serious Treatment-Emergent Adverse Events by System Organ Class and MedDRA Preferred Term
- CT-8.3.1 Incidence of Potentially Drug-Related TEAEs by System Organ Class and MedDRA Preferred Term (Safety Sample)
- CT-8.3.2 Incidence of Potentially Drug-Related TEAEs by System Organ Class, MedDRA Preferred Term and Severity (Safety Sample)
- CT-8.4 Incidence of Deaths Due to TEAEs by System Organ Class and MedDRA Preferred Term (Safety Sample)
- CT-8.5.1 Incidence of Serious TEAEs by System Organ Class and MedDRA Preferred Term (Safety Sample)
- CT-8.5.2 Incidence of Serious TEAEs by System Organ Class, MedDRA Preferred Term and Severity (Safety Sample)
- CT-8.6.1 Incidence of TEAEs Resulting in Discontinuation from Study by System Organ Class and MedDRA Preferred Term (Safety Sample)
- CT-8.6.2 Incidence of TEAEs Resulting in Discontinuation from Study by System Organ Class, MedDRA Preferred Term and Severity (Safety Sample)
- CT-8.7.1 Incidence of Treatment-Emergent Adverse Events of Special Interests (AESIs) by System Organ Class and MedDRA Preferred Term (Safety Sample)

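### SAP 9.1 summarises the long-term TEAE endpoint without time at risk; adding time-at-risk outputs is a cheap improvement, mainly for late-onset events

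*SAP*

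**What the plan says.** Protocol 3.5.1 makes long-term safety and tolerability the primary endpoint, judged by how often TEAEs occur and how severe they are. SAP 9 repeats this: "The primary safety endpoint analysis is the frequency and severity of AEs in the open-label treatment period".

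For the analysis, Protocol 7.4.1 states "The incidence of TEAEs will include the following summaries" and lists the categories. SAP 9.1 follows: "The incidence of the following events in the open-label treatment phase will be summarized using the Safety Sample". The Safety Sample is everyone with at least one dose (SAP 5.1). No formula for incidence is given; I read it as the percentage of dosed subjects with the event. SAP 9.1 also says: "Adverse events occurring up to 30 days after the last day of IMP will be included in the summary tables".

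In the proposed table list (SAP 12), CT-8.2.8 to CT-8.2.10 add numbers of events without person-time. Completion by week (CT-1.3) and exposure (SAP 9.9, CT-7.1, CT-7.2) are reported separately from AEs. CT-9.1 to CT-9.3 are listings.

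On retention, Protocol 3.3.1 expects that "at least 300 subjects will achieve 6-month exposure and 100 subjects will achieve 52-week exposure", out of about 720. Protocol 7.1 gives no dropout rate: "The sample size is not based on statistical power considerations but on ICH/GCP requirements".

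**The concern.** A subject who leaves at week 10 stays in the denominator for all 52 weeks but can contribute events only while observed. The crude percentage then falls below the risk of someone treated for the full year. Events that appear late lose most, and those are what this trial can show and the 6-week parent trials cannot.

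The planned tables do not let a reader repair this. Attrition and AEs appear in separate marginal tables, so the risk of first onset in weeks 26-52 cannot be recovered. Safety results are also shown by parent-treatment group, de novo and overall (SAP 9). If retention differs between those columns, crude percentages will differ through time at risk alone.

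**Working it through.** **Inputs from the documents.** Enrolment is about 720 (Protocol 3.3.1), with components of 560 and 145 (Protocol 7.1, SAP 4). 560 + 145 = 705, which is 15 below 720 (15/720 = 2.1%) and consistent with an approximate total. The exposure expectations are 300/720 = 41.7% and 100/720 = 13.9%. They cannot be derived from anything else in the plan.

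**Assumptions.** True 52-week risk 10%; dropout independent of the event; retention at 6 and 12 months as in the table; no post-dose window.

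**Formula.** Expected crude incidence is the integral over 52 weeks of f(t) x S(t), where f is the density of first onset and S the fraction still observed. Write S26 and S52 for retention at 6 and 12 months, and F(26) and F(52) for true cumulative risk. Moving all leavers to the start or the end of their half-year gives bounds:

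- low = (S26 - S52) x F(26) + S52 x F(52)
- high = (1 - S26) x F(26) + S26 x F(52)

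For a constant hazard, F(26) = 1 - 0.9^0.5 = 5.13% and F(52) = 10%. For risk in weeks 26-52 only, F(26) = 0, so the bounds are S52 x 10% and S26 x 10%.

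**Example, 80%/70%.** Low = 0.10 x 5.13 + 0.70 x 10 = 7.5%. High = 0.20 x 5.13 + 0.80 x 10 = 9.0%. Late-only: 7.0% to 8.0%.

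| Retention at 6/12 months | Constant hazard: bounds (gradual leaving) | Weeks 26-52 only: bounds (gradual leaving) |
|---|---|---|
| 90%/85% | 8.8-9.5% (9.1%) | 8.5-9.0% (8.8%) |
| 80%/70% | 7.5-9.0% (8.3%) | 7.0-8.0% (7.5%) |
| 60%/40% | 5.0-8.1% (6.4%) | 4.0-6.0% (5.0%) |
| 300 and 100 of 720 | 2.8-7.2% (4.7%) | 1.4-4.2% (2.6%) |

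Gradual leaving means piecewise-exponential dropout through the two retention values.

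**Early events.** For a 10% risk confined to the first 4 weeks, gradual leaving in the bottom-row case still gives 9.4%. It would fall much further only if leaving were bunched into those same weeks.

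**Post-dose window.** At 80%/70% with gradual leaving, counting events to 10 or 30 days after last dose moves 8.25% to 8.33% or 8.49%, and late-only 7.50% to 7.55% or 7.67%. The timing of leaving matters more.

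**Base of 705.** Bottom-row case: (200 x 5.13 + 100 x 10)/705 = 2.9% and (405 x 5.13 + 300 x 10)/705 = 7.2%. Late-only: 1.4-4.3%. Little changes.

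**The case against.** The strongest reply is that the plan does what it promises. The endpoint is frequency and severity, protocol and SAP both specify incidence, and the SAP delivers it. Crude incidence validly describes what happened under actual use. The shortfall exists only against the risk had everyone stayed on treatment, which the plan never names as its target. All of that stands, and it is why this is a recommended supplement. It does not answer the long-term objective, which the separate completion and exposure tables also leave open.

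A reader might infer that the plan is wrong or contradicts itself. It is not and does not: no 52-week-risk estimand is stated. A reader might also take 300 and 100 of 720 as a retention forecast and conclude that more than half of the 52-week risk will be missed. The documents do not support that. Protocol 3.3.1 words the first figure as a minimum, the synopsis calls both approximate, and neither is tied to a dropout rate. That row is an extreme case.

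Added methods are not a cure either. Kaplan-Meier recovers the 10% when dropout is independent of events, which merely restates the assumption. The assumption is doubtful where AEs drive leaving; rash is a listed discontinuation reason (Protocol 3.8.3.3).

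Finally, parts of the SAP are removed or redacted, so the statement covers the visible text only.

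**Conclusion.** The point holds as an inexpensive improvement that should be made. Confidence in the direction is high: events that would have occurred after a subject leaves can only lower the crude percentage relative to full follow-up. The size is unknown. It rests on assumed retention, onset pattern and time of leaving, and on independent dropout. For a true risk of 10%, the expected shortfall runs from about 0.5 to 1.5 percentage points at 90%/85% retention to between 1.9 and 6.0 points at 60%/40%, across both onset patterns. With full retention it is zero. For events in the first weeks it is small unless subjects leave in those same weeks.

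**What to change.** Keep all planned tables. Add to SAP 9.1, for overall, severe and serious TEAEs, TEAEs leading to discontinuation, skin AESIs and abuse-related TEAEs:

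1. First-event incidence per 100 person-years with an exact Poisson 95% CI.
2. Kaplan-Meier cumulative incidence at Weeks 26 and 52.
3. TEAEs by onset interval (for example 0-12, >12-26 and >26-52 weeks), with number at risk and person-time. Person-time is needed because subjects also leave within an interval. Dividing late-only events by the number at risk at week 26 gives, with gradual leaving, 8.75/0.90 = 9.7%, 7.50/0.80 = 9.4%, 4.95/0.60 = 8.3% and 2.55/0.417 = 6.1% in the four cases, still short of 10%.

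**Individual PTs.** Give the onset-interval table without the crude 5% cut-off of CT-8.2.3. A 10% risk in weeks 26-52 would show as 4.0-6.0% at 60%/40% and 1.4-4.2% in the extreme case, so that screen can drop the very terms sought. Show all PTs, or at least those in CT-8.2.7 (2%) plus any reaching 2% of subjects at risk in any interval.

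**Window.** Use first dose to last dose plus 10 days for numerator, person-time and censoring. Active monitoring ends there (Protocol 3.7.1.3, 5.9.2). Later events up to 30 days stay in the crude tables. Using 30 days could add up to 720 x 20/365 = 39 person-years without active monitoring, about 12% of the 331 in the extreme case.

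**Presentation.** Follow SAP 9's columns, count time from first open-label dose, and note that some rollovers had earlier exposure. Show TEAEs leading to discontinuation with and without COVID-19 discontinuations, because the addendum (2.4) records positive or presumed-positive cases as AE discontinuations.

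**Sensitivity.** Treat discontinuation due to a different TEAE as a competing event where that is not empty. It is empty for overall TEAEs and for TEAEs leading to discontinuation.

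**Cost.** At most 3 x 6 = 18 outputs, fewer if combined, plus the PT table, the COVID-19 split and the sensitivity analysis, all from dates already collected. The SAP must state the reliance on non-informative dropout and, for the person-year rate, on a constant hazard. The outputs reduce the problem but do not remove it.

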#### Adverse Events of Special Interest

Newly acquired skin eruptions that are non-traumatic will be considered AESIs. These may include but are not limited to eruptions such as skin rashes, skin irritations, skin reactions, or acneiform lesions. This does not include localized contact irritation at ECG lead sites due to application or removal of lead adhesive.

Refer to the separate rash workup plan for complete details, including reporting forms, and extra measures that must be performed to characterize any skin AESI of a newly acquired skin eruption that is non-traumatic. The trial site will have a local designated dermatologist available for immediate consultation during the trial for these AESIs.

## 9.2 Clinical Laboratory Tests

Summary statistics for mean and mean change from baseline in the routine clinical laboratory measurements, HbA1c, TSH, and PT/INR will be provided. Potentially clinically relevant results in laboratory tests will also be summarized.

Potentially clinically relevant laboratory measurement test results in the open-label treatment period will be identified, summarized, and listed. Criteria for identifying laboratory values of potential clinical relevance are provided in Appendix 2.

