# **11 Potential Clinical Relevance Criteria from Protocol**

Appendix 1 C	Criteria for Identifying Vital Signs of Potential Clinical Relevan			
Variable	Criterion Value a	Change Relative to Baseline a		
Heart Rate b	> 100 bpm < 50 bpm	≥ 10 bpm increase ≥ 10 bpm decrease		
Systolic Blood Pressure b	≥ 140 mmHg < 90 mmHg	≥ 20 mmHg increase ≥ 20 mmHg decrease		
Diastolic Blood Pressure b	≥ 90 mmHg < 60 mmHg	$\geq$ 10 mmHg increase $\geq$ 10 mmHg decrease		
Orthostatic Hypotension	
 
≥ 30 mmHg decrease in systolic blood pressure and/or a ≥ 20 mmHg
 
in diastolic blood pressure after at least
 
3 minutes of standing compared to the previous supine blood pressure.
 
	Not Applicable (baseline status not considered)		
Orthostatic Tachycardia	≥ 25 bpm increase in heart rate from supine to standing	Not Applicable (baseline status not considered)		
Weight	-	≥ 7% increase ≥ 7% decrease		

a In order to be identified as potentially clinically relevant, an on-treatment value must meet the "Criterion Value" and also represent a change from the subject's baseline value of at least the magnitude shown in the "Change Relative to Baseline" column.

b As defined in "Supplementary Suggestions for Preparing an Integrated Summary of Safety Information in an Original NDA Submission and for Organizing Information in Periodic Safety Updates," FDA Division of Neuropharmacological Drug Products draft (2/27/87).

Relevance			
Laboratory Tests	Criteria		
Chemistry			
AST (SGOT)	$\geq$ 3 x upper limit of normal (ULN)		
ALT (SGPT)	$\geq 3 \text{ x ULN}$		
Alkaline phosphatase	$\geq$ 3 x ULN		
BUN	$\geq$ 30 mg/dL		
Creatinine	$\geq 2.0 \text{ mg/dL}$		
Uric Acid	-		
Men	$\geq 10.5 \text{ mg/dL}$		
Women	$\geq 8.5 \text{ mg/dL}$		
Bilirubin (total)	$\geq 2.0 \text{ mg/dL}$		
Creatine Phosphokinase (CPK)	> 3  x ULN		
Hematology			
Hematocrit			
Men	$\leq$ 37 % and decrease of $\geq$ 3 percentage points from Baseline		
Women	$\leq$ 32 % and decrease of $\geq$ 3 percentage points from Baseline		
Hemoglobin			
Men	$\leq 11.5 \text{ g/dL}$		
Women	$\leq$ 9.5 g/dL		
White blood count	$\leq 2,800/$ mm  or $\geq 16,000/$ mm 		
Eosinophils	≥ 10%		
Neutrophils	$\leq 15\%$		
Absolute neutrophil count	$\leq$ 1,500/ mm 		
Platelet count	$\leq$ 75,000/ mm  or $\geq$ 700,000/ mm 		
Urinalysis			
Protein	Increase of $\geq 2$ units		

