Glucose	Increase of $\geq 2$ units		
Additional Criteria			
Chloride	$\leq$ 90 mEq/L or $\geq$ 118 mEq/L		
Potassium	$\leq 2.5 \text{ mEq/L}$ or $\geq 6.5 \text{ mEq/L}$		
Sodium	$\leq 126 \text{ mEq/L}$ or $\geq 156 \text{ mEq/L}$		
Calcium	$\leq 8.2 \text{ mg/dL} \text{ or} \geq 12 \text{ mg/dL}$		
Glucose			
Fasting	$\geq 100 \text{ mg/dL}$		
Non-Fasting	$\geq 200 \text{ mg/dL}$		
Total Cholesterol, Fasting	$\geq 240 \text{ mg/dL}$		
LDL Cholesterol, Fasting	$\geq 160 \text{ mg/dL}$		
HDL Cholesterol, Fasting	-		
Men	< 40 mg/dL		
Women	< 50  mg/dL		
Triglycerides, Fasting	$\geq 150 \text{ mg/dL}$		

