- CT-8.7.2 Incidence of Treatment-Emergent Adverse Events of Special Interests (AESIs) by System Organ Class and MedDRA Preferred Term and Severity (Safety Sample)
- CT-8.8.1 Incidence of Treatment-Emergent Abuse Potential-Related Adverse Events by System Organ Class and MedDRA Preferred Term (Safety Sample)
- CT-8.8.2 Incidence of Treatment-Emergent Abuse Potential-Related Adverse Events by System Organ Class and MedDRA Preferred Term and Severity (Safety Sample)
- CT-9.1 Listing of Deaths
- CT-9.2 Listing of Serious Adverse Events
- CT-9.3 Listing of Discontinuations of Study Medications Due to Adverse Events
- CT-10.1 Criteria for Laboratory Test Values with Potential Clinical Relevance
- CT-10.2.1 Listing of Laboratory Test Values with Potential Clinical Relevance by Subject (Safety Sample)
- CT-10.2.2 Listing of Laboratory Test Values with Potential Clinical Relevance by Test (Safety Sample)
- CT-10.2.3 Incidence of Laboratory Test Values with Potential Clinical Relevance (Safety Sample)

Confidential - Proprietary Information 27 15 September 2021 Until the information herein is released by Otsuka to the public domain, the contents of this document are Otsuka confidential information and should not be duplicated or re-distributed without prior written consent of Otsuka. 27

- CT-10.3.1 Mean Change from Baseline in Clinical Laboratory Test Results Serum Chemistry (Safety Sample)
- CT-10.3.2 Mean Change from Baseline in Clinical Laboratory Test Results Hematology (Safety Sample)
- CT-10.3.3 Mean Change from Baseline in Clinical Laboratory Test Results Urinalysis (Safety Sample)
- CT-10.3.4 Mean Change from Baseline in Clinical Laboratory Test Results Other Tests (Safety Sample)
- CT-10.4.1 Incidence of Potentially Liver Injury Related Laboratory Test Abnormalities (Safety Sample)
- CT-10.4.2 Listing of Potentially Liver Injury Related Laboratory Test Abnormalities (Safety Sample)
- CT-11.1 Criteria for Potentially Clinically Relevant Abnormalities in Vital Signs
- CT-11.2.1 Listing of Potentially Clinically Relevant Abnormalities in Vital Signs (Safety Sample)
- CT-11.2.2 Incidence of Potentially Clinically Relevant Abnormalities in Vital Signs (Safety Sample)
- CT-11.2.3 Mean Change from Baseline in Vital Signs (Safety Sample)
- CT-11.3 Mean Change from Baseline in Body Weight (kg) (Safety Sample)
- CT-11.4 Mean Change from Baseline in Waist Circumference (cm) (Safety Sample)
- CT-11.5 Mean Change from Baseline in BMI (kg/m2) (Safety Sample)

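### The laboratory incidence table counts values already abnormal at baseline together with new ones, chiefly for fasting glucose and lipids

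*SAP*

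**What the plan says.** SAP Section 9.2 sets the rule: "Potentially clinically relevant laboratory measurement test results in the open-label treatment period will be identified, summarized, and listed". It then points to the cut-offs: "Criteria for identifying laboratory values of potential clinical relevance are provided in Appendix 2". The output is table CT-10.2.3 in SAP Section 12, "Incidence of Laboratory Test Values with Potential Clinical Relevance", on the Safety Sample.

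In Appendix 2, three tests refer to baseline. Hematocrit needs a limit plus a fall of at least 3 "percentage points from Baseline". Urine protein and urine glucose are themselves defined by a change, "Increase of $\geq 2$ units". The other tests, for example "HDL Cholesterol, Fasting" and "Triglycerides, Fasting", have a cut-off only.

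Most other safety summaries in the SAP do use baseline:

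- The vital-sign and ECG tables share a footnote that begins "In order to be identified as potentially clinically relevant, an on-treatment value must meet the" and goes on to require both the listed value and a stated change from baseline.
- The new-onset QT/QTc categories in Section 9.4 exclude values already present at baseline.
- Emergent suicidality in Section 9.5 requires none at baseline.
- Treatment-emergent adverse events in Section 9.1 must be new, or continuing from baseline with worsening or another listed feature.

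Where the vital-sign table sets baseline aside on purpose (the orthostatic criteria), it says so. The laboratory table has neither a baseline condition nor such a statement. Protocol Section 7.6.2 leaves the criteria to the SAP and adds no baseline rule.

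**The concern.** A table headed incidence, in a single-arm trial whose objective is long-term safety, will be read as what happened on treatment. As specified, it mixes three groups: subjects abnormal before the first open-label dose who stayed so, subjects who became abnormal, and subjects who crossed a limit by ordinary variation. With no control arm, the reader cannot subtract the first or the third. A high percentage for fasting glucose or triglycerides could then reflect the population enrolled, and a modest drug effect would be hard to see against it.

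**Working it through.** **1. Count of tests.** Sex-specific and fasting/non-fasting lines are counted once. Chemistry 8, hematology 7, urinalysis 2, additional 9: 8 + 7 + 2 + 9 = 26. With a baseline element: hematocrit, urine protein, urine glucose = 3. Without: 26 − 3 = 23, and 23/26 = 88%.

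**2. Where the missing condition has consequences.** The flag limits (SAP Appendix 2) are set against the entry exclusions (Protocol Tables 3.4.3.1-1 and 3.4.3.2-1):

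| Test | Flagged at | Excluded at entry | Can be flagged yet eligible |
|---|---|---|---|
| AST, ALT | ≥ 3 × ULN | > 2 × ULN | no |
| Platelets (low) | ≤ 75,000/mm³ | ≤ 75,000/mm³ | no |
| Creatinine | ≥ 2.0 mg/dL | ≥ 2 (rollover), > 2 (de novo) | only exactly 2 mg/dL, de novo |
| Hemoglobin, men | ≤ 11.5 g/dL | ≤ 9 g/dL | above 9 up to 11.5 |
| Absolute neutrophils | ≤ 1,500/mm³ | ≤ 1,000/mm³ | above 1,000 up to 1,500 |
| Fasting glucose | ≥ 100 mg/dL | no general limit; ≤ 125 required of diabetic de novo subjects retested fasting | yes |
| Total, LDL, HDL cholesterol; triglycerides | Appendix 2 limits | none | yes |

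Even exclusionary values can be present in treated subjects, because Protocol Section 3.7.4.2 says baseline results arrive after dosing has begun and continuation is then discussed with the medical monitor.

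**3. Size.** The SAP states no figure for this table, so there is nothing to reproduce. Let b be the share meeting a criterion at baseline, s the share of those still meeting it on treatment, and q the share of the others who newly meet it. Then

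table figure = b·s + (1 − b)·q.

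The documents give none of the three; all values below are assumptions. For counts, N = 560 + 145 = 705 (SAP Section 4).

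- b = 20%, s = 80%, q = 5%: 0.20 × 0.80 + 0.80 × 0.05 = 0.16 + 0.04 = 20.0%, about 141 of 705. Of those counted, 0.16/0.20 = 80% already met the criterion at baseline. Among the 0.80 × 705 = 564 who did not, the figure is 5%, about 28 subjects.
- q = 5%, b from 1% to 30%, s from 60% to 100%: from 0.01 × 0.60 + 0.99 × 0.05 = 5.6% to 0.30 × 1.00 + 0.70 × 0.05 = 33.5%.
- q = 0, same ranges: from 0.01 × 0.60 = 0.6% to 0.30 × 1.00 = 30.0%, with no new case at all.

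**4. What a baseline condition does not remove.** Take fasting glucose as normal with no drug effect, mean 90 to 95, between-subject SD 8 to 9 and within-subject SD 6 mg/dL (assumptions). The SD of one measurement is √(64 + 36) = 10 to √(81 + 36) = 10.8. The share at or above 100 at baseline is then 1 − Φ(10/10) = 16% to 1 − Φ(5/10.8) = 32%. Two measurements on one subject correlate at 64/100 = 0.64 to 81/117 = 0.69. Under that bivariate normal model, about 10% to 17% of subjects below 100 at baseline are at or above it on a single later draw. More draws raise this share.

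**The case against.** **The word.** The SAP never calls these results treatment-emergent. Protocol Section 7.6.2 speaks of laboratory values and Section 7.6.4 of ECG changes, and the table titles keep that distinction, so CT-10.2.3 counts what its title says. This stands against any inference that the SAP attributes the values to drug. It does not remove the mixing: Protocol Section 3.5.4 frames the additional safety variables as clinically significant changes, which this table does not isolate.

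**The population.** A reader might infer that BMI up to 40 and stable diabetes are admitted throughout. The documents do not support that. Both are de novo criteria, covering about 145 of 705 planned subjects (21%). For the roughly 560 rollover subjects this protocol sets no such rule, and their original criteria are in parent protocols not available here. Only the HbA1c limit of about 7% applies to both groups.

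**The number of tests.** It is tempting to treat all 23 as equally affected. They are not: step 2 shows little room for AST, ALT, platelets and creatinine. Extreme sodium or potassium limits would rarely be met at entry, and investigators may exclude medically significant results by judgment.

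**Other outputs.** Mean change is planned for laboratory tests including HbA1c, and for weight, waist circumference and BMI. Protocol Section 5.1 has investigators judge abnormal results against baseline and record medically relevant ones as adverse events, which enter the primary analysis with its own baseline rule. So it would be too strong to say that a metabolic signal must go unseen. None of these outputs, however, separates new from pre-existing abnormality in CT-10.2.3. The value listings (CT-10.2.1 and CT-10.2.2) leave that to the reader, and Section 12 lists no laboratory shift table.

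**The remedy.** Restricting to subjects below the limit at baseline leaves chance crossings (step 4) and drops worsening in those already abnormal. This stands, and is why shift counts are also needed.

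**Conclusion.** The point holds for a descriptive, non-primary table. For 23 of 26 tests the rule is a cut-off alone, and the table pools subjects who met it before the first open-label dose with those who met it afterwards. The practical weight lies on fasting glucose and the four lipid measures, with a smaller effect for hemoglobin in men and absolute neutrophils.

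The count of 23 comes directly from Appendix 2. The 20% against 5% is illustrative: it rests on assumed b, s and q, and the 5% is itself one of those inputs. A reader might take either figure as a forecast for this trial; the documents contain no laboratory distributions that would support one. Nor do they support reading the point as a flaw in the primary adverse-event analysis. The change is worth making because safety is the trial's objective, there is no comparator, and the baseline values needed are already defined (SAP Section 7.1) and collected.

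**What to change.** - In SAP Section 9.2, define the numerator of CT-10.2.3 as subjects who meet the criterion on treatment and did not meet it at baseline. Define the denominator as subjects who did not meet it at baseline and have a post-baseline value for that test.
- Add a column with the number already meeting the criterion at baseline.
- Add baseline-by-worst-value shift counts for at least fasting glucose, total, LDL and HDL cholesterol and triglycerides. These keep worsening in subjects abnormal at baseline visible and let chance crossings be judged.
- Leave every threshold in Appendix 2 as it is.

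The cost is a short SAP amendment, denominators that differ by test, and a small amount of programming for the revised table and the shift tables. No new data are needed.
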